6. DATA CONVENTIONS

The following analysis conventions will be used in the statistical analysis.

6.1. Definition of Baseline for Efficacy/Safety Variables

Unless otherwise specified, the baseline measurement for all measurements will be the latest available valid measurement taken prior to the administration of study drug. If any randomized participants are not treated, the baseline will be the last value on or prior to the randomization. The following rules specify the determination by both date/time information:

1. For the AE, lab (including biomarker), drug concentration and ADA data, both date and time of the measurement will be used to determine baseline by comparing with the first infusion date and time.
2. For other data except AE, lab (including biomarker), drug concentration or ADA, only date of measurement will be used to determine baseline by comparing with the first infusion date.

For the rescreened participants, all data from the same participant will be used to derive baseline regardless if the data is from the screen- failure subject ID or enrolled subject ID.

6.2. General Data Handling Conventions

For the laboratory safety variables and biomarker data, if the data below the lower limit of quantification (LLOQ) / limit of linearity, half of the lower limit value (i.e., LLOQ/2) will be used for quantitative analyses. For data above the upper limit of quantification (ULOQ) / limit of linearity, the upper limit value (i.e., ULOQ) will be used for quantitative analyses.

6.3. Data Handling Convention for Missing Data

Missing data will not be imputed in listing. This section includes the methods for missing data imputation for some summary analyses, if necessary.

Adverse event

If the intensity of a TEAE is missing, it will be classified as “severe” in the frequency tables by intensity of TEAEs. If the assessment of relationship of a TEAE to the investigational product is missing, it will be classified as related to the investigational product.

Missing date

Every effort will be made to collect the start dates of all AEs and concomitant medications/procedures. However, in the case the start date of an AE or concomitant medication is incomplete or missing, it will be assumed to have occurred on or after the first dose of study medication, except if an incomplete date (e.g., month and year) clearly indicates that the event started prior to treatment. If the partial date indicates the same month or year of the first dose of study medication date, then the start date of the first dose will be imputed, otherwise, the missing day or month by the first day or the first month will be imputed.

Potentially Clinically Significant Value (PCSV)

If a participant has a missing baseline value, this participant will be grouped in the category “normal/missing at baseline”.

For PCSVs with 2 conditions, one based on a change from baseline value and the other on a threshold value or a normal range, with the first condition being missing, the PCSV will be based only on the second condition.

For a PCSV defined on a threshold and/or a normal range, this PCSV will be derived using this threshold if the normal range is missing; e.g., for eosinophils the PCSV is >0.5 giga/L or $>\text{ULN}$ if $\text{ULN} \geq 0.5$ giga/L. When ULN is missing, the value 0.5 should be used.

Measurements flagged as invalid by the laboratory will not be summarized or taken into account in the computation of PCSVs.

For laboratory results below the quantifiable LOQ, half of the LOQ will be imputed for calculating the descriptive summary.

No imputations for missing laboratory data, ECG data, vital sign data, or physical examination data will be made.

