4. ANALYSIS VARIABLES

4.1. Demographic and Baseline Characteristics

The following demographic variables will be summarized by treatment group:

- Age at screening (year)
- Age categories (<70, \geq 70)
- Sex (Male, Female)
- Race (American Indian/Alaskan Native, Asian, Black/African American, Native Hawaiian/Other Pacific Islander, White and Other)
- Ethnicity (Hispanic/Latino, Not Hispanic or Latino)
- Weight (kg)
- Height (cm)
- Body mass index (BMI) (kg/m²)

Other baseline characteristics may include:

- Medication history (antiplatelets; NSAIDs; hormone replacement therapy)
- aPTT (sec)
- PT (sec)
- FXI functional activity level
- TKA information (including but not limited to operative leg, blood loss during surgery, and type of anesthesia)

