4.5.2. Bleeding Events

The ISTH criteria will be used for both major bleeding events and CRNM events as described below. Minimal bleeding will be captured separately as an exploratory endpoint.

Major bleeding, CRNM bleeding and minimal bleeding through time of venography (or day 12, whichever is earlier) and through the end of study will be summarized by each treatment group.

Major Bleeding (ISTH):

- Fatal bleeding and/or
- Bleeding that is symptomatic and occurs in a critical area or organ, such as intracranial, intraspinal, intraocular, retroperitoneal, pericardial, in a non-operated joint, or intramuscular with compartment syndrome, assessed in consultation with the surgeon, and/or
- Overt extra surgical site bleeding causing a fall in hemoglobin level of 20 g/L (1.24 mmol/L) or more, or leading to transfusion of two or more units of whole blood or packed red cells, with temporal association within 24 to 48 hours to the bleeding, and/or
- Surgical site bleeding that requires a second intervention (open, arthroscopic, endovascular) or a hemarthrosis of sufficient size as to interfere with rehabilitation by delay

in mobilization or delayed wound healing, resulting in prolonged hospitalization or a deep wound infection, and/or

- Surgical site bleeding that is unexpected and prolonged and/or is sufficiently large to cause hemodynamic instability, as assessed by the surgeon. There should be an associated fall in hemoglobin level of at least 20 g/L (1.24 mmol/L), or transfusion indicated by the bleeding, of at least two units of whole blood or red cells, with temporal association within 24 hours to the bleeding.

Clinically Relevant Non-Major Bleeding (ISTH):

- Any sign or symptom of hemorrhage (e.g., more bleeding than would be expected for a clinical circumstance, including bleeding found by imaging alone) that does not fit the criteria for the ISTH definition of major bleeding but does meet at least one of the following criteria:
 - requiring medical intervention by a healthcare professional
 - leading to hospitalization or increased level of care
 - prompting a face to face (i.e., not just a telephone or electronic communication) evaluation

Minimal Bleeding:

Any overt bleeding event that does not meet the criteria for either major or CRNM bleeding will be categorized as a minor bleeding event. Minimal bleeding will be captured separately as an exploratory endpoint.

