5.8.2. Assessment for Bleeding

Participants will be assessed for surgical site bleeding events at time points according to [Table 3](#). Description of surgical site bleeding events will include the following: onset and duration; associated clinical symptoms (if any) and sequelae, including prolonged hospitalization or deep wound infection; requirement for additional surgical or interventional procedure.

Participants will also be assessed for overall bleeding events at time points according to [Table 3](#). Description of bleeding events will include the following: location; onset and duration; associated symptoms (if any); precipitating factors (if any).

For all bleeding events (surgical and extra surgical), the following will be recorded: associated changes in hemoglobin, hematocrit; requirement for, timing of, and quantity of transfusion.

In addition, for all participants, peri- and post-operative blood loss will be recorded, as per local practice.

All bleeding events will need to be recorded as an AE with documentation sent to the central AC as instructed in the Study Manual for Venography and Event Reporting. Events will be classified by the AC using the ISTH criteria for both major ([Schulman, 2010](#)) and CRNM ([Kaatz, 2015](#)) bleeds as described in [Section 4.5.2](#).

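### Read literally, the SAP's partial-date rule moves an adverse event dated to a later month of the dosing year back to the first-dose date, so a late bleed can enter the day-12 bleeding summary

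*SAP*

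**What the plan says.** SAP 6.3 (paragraph on missing dates) applies "in the case the start date of an AE or concomitant medication is incomplete or missing". It has two steps.

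1. The event is assumed to have begun on or after first dose, "except if an incomplete date (e.g., month and year) clearly indicates that the event started prior to treatment".
2. A second test follows: "If the partial date indicates the same month or year of the first dose of study medication date". When it is met, the event takes the first-dose date as its start. When it is not, a missing day becomes the 1st of the month and a missing month becomes January.

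The same section says "Missing data will not be imputed in listing". Imputation is for some summaries, where needed.

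The link to an endpoint is as follows. SAP 5.8.2 says "All bleeding events will need to be recorded as an AE". SAP 4.5.2 summarises "Major bleeding, CRNM bleeding and minimal bleeding through time of venography (or day 12, whichever is earlier) and through the end of study" by treatment group. Major and clinically relevant non-major bleeding over the earlier window is a secondary endpoint in Protocol 4.1.2.

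**The concern.** The condition joins month and year with *or*. A start date with month and year known and only the day missing therefore passes whenever the year matches, whatever the month. The recorded month is discarded, and the first-of-month branch is left for dates in another calendar year.

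For most adverse events this would only blur the timing. For bleeds it matters more, because the start date can decide whether an event belongs to the venography/day-12 summary or only to the end-of-study summary. Protocol Table 2 schedules the last bleeding assessments at days 10, 30 and 75. The final recall interval is thus about 45 days, in which a month-only date is plausible. Exposure after day 12 also differs by arm: Protocol 8.8.2 permits continued prophylaxis for the comparators, and Protocol 3.2.1 expects aPTT to stay raised on REGN9933 through at least day 35. Misplaced late bleeds need not balance across arms, and the direction is unknown.

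The rule also never looks at the stop date, so an imputed start can fall after the event has ended.

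**Working it through.** The documents state no figure for this rule, so there is none to reproduce. The check applies the rule to worked dates and then enumerates it.

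**Inputs from the documents.** Day 1 is the day of surgery and dosing starts 12 to 24 hours after it ends (SAP 2.1), so first dose is on day 1 or 2. Follow-up runs to day 75 (Protocol 6.1).

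**Assumptions.** Surgery dates are uniform over one calendar year. True onset is uniform on days 13 to 75. Month and year are known and the day is missing.

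**Worked dates**, first dose on the day after surgery:

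| Surgery | True onset | Recorded as | Literal rule | Month and year must match |
|---|---|---|---|---|
| 10 Mar 2023 | 15 May 2023 (day 67) | May 2023 | 11 Mar (day 2) | 1 May (day 53) |
| 10 Mar 2023 | 20 Apr 2023 (day 42) | Apr 2023 | 11 Mar (day 2) | 1 Apr (day 23) |
| 10 Dec 2023 | 20 Jan 2024 (day 42) | Jan 2024 | 1 Jan (day 23) | 1 Jan (day 23) |
| 28 Mar 2023 | 20 Apr 2023 (day 24) | Apr 2023 | 29 Mar (day 2) | 1 Apr (day 5) |

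Rows 2 and 3 have the same true delay. The literal rule sends one to day 2 and the other to day 23 only because the second crosses a year boundary. Row 4 shows that the corrected rule can still place a late event early.

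**Enumeration.** There are 365 surgery dates × 63 onset days = 22,995 cases. Share misplaced = cases imputed to day 12 or earlier ÷ all cases.

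| | First dose day 1 | First dose day 2 |
|---|---|---|
| Literal rule, all cases | 20,561 / 22,995 = 89.4% | 20,604 / 22,995 = 89.6% |
| Month and year must match, all cases | 5,373 / 22,995 = 23.4% | 5,373 / 22,995 = 23.4% |
| Literal rule, later-month cases only | 18,411 / 20,845 = 88.3% | 18,221 / 20,612 = 88.4% |
| Month and year must match, later-month cases only | 3,223 / 20,845 = 15.5% | 2,990 / 20,612 = 14.5% |

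The remaining 23.4% has two parts. Same-month events go to first dose under either rule (22,995 − 20,845 = 2,150 with first dose on day 1). Later-month events whose first of the month falls by day 12 add 3,223. Together, 2,150 + 3,223 = 5,373.

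**From shares to events.** The difference is about 89.5% − 23.4% = 66 percentage points, or 0.66 of an event per late bleed with a missing day. The documents do not say how many such bleeds to expect. As an illustration only, 30 late bleeds over all arms with 1% to 5% lacking a day gives 0.3 to 1.5 such bleeds, and 0.66 × 0.3 to 0.66 × 1.5 = 0.2 to 1.0 events wrongly moved that the correction would prevent. Incidence is counted per participant, so a person who had already bled by day 12 adds nothing.

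**Stop date.** Take first dose on 11 March and an adverse event recorded as starting in March and stopping on 5 March. Month and year match, so the start is imputed as 11 March, six days after the event ended. Events are collected from consent (SAP 4.5.1), so such a record can exist. The exception in SAP 6.3 considers only what the incomplete date shows, and March alone does not show a start before 11 March. The event is then treated as on or after first dose and counted as treatment-emergent. This happens under either reading of *month or year*.

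**The case against.** The strongest reply is that the sentence can be read respectively: compare the month when the day is missing, and the year when the month is missing. The parallel wording of the following clause ("then the start date of the first dose will be imputed, otherwise, the missing day or month by the first day or the first month") supports that. Taken literally, the same month of a different year would also pass, which cannot be intended. This stands as a possible reading, so misclassification is not certain. But the SAP does not say it, and a programmer following the text could code either version.

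The bleeds that matter most are also the least likely to lack a day. Onset and duration are recorded (SAP 5.8.2), moderate-to-severe bleeding is reportable within 24 hours (Protocol 10.1.3), and narratives ask for onset dates, which may be estimates (Protocol 10.1.2.1). The SAP does not expressly say that imputed dates assign adjudicated bleeds to a window. This limits the size. It does not remove the problem: the adjudication committee's stated task is to interpret and classify events, and no text says it sets onset dates.

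Three stronger inferences are tempting, and the documents do not support them.

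- *Earlier-month dates are also pulled onto the dosing day.* A February event or drug with dosing in May is covered by the exception in the preceding sentence, which gives month and year as its example. With the exception applied, none of the enumerated earlier-month dates in the 30 days before surgery becomes on-treatment. Only the order of precedence needs stating.
- *Medications are moved into a day-12 analysis.* SAP 5.3 summarises them by treatment group and ATC level with no day-12 split, and SAP 4.1 does not derive medication history from an imputed start date.
- *The efficacy result or treatment-emergent counts shift with later-month dates.* The rule is not stated to apply to adjudicated VTE, and an event in a later month is after first dose either way.

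**Conclusion.** Wrong as written, minor. On its literal reading the rule resets a day-missing adverse event in a later month of the dosing year to the first-dose date, and no other SAP text corrects this. The one analysis where it can matter is the bleeding summary through venography or day 12. The contrast of about 90% against 23% rests on uniform surgery and onset dates and applies only to events whose day is missing. It describes how the rule behaves, not how many bleeds would be affected. With no frequency of partial dates in the documents, zero to about one event is the realistic range, and it would be noticeable only if bleeding counts per arm are small.

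The missing stop-date check is a separate, smaller defect that can add to treatment-emergent counts whichever reading is taken. A reader might infer that the bleeding endpoint is unreliable; the evidence supports only a drafting error to correct before the derivation is programmed.

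**What to change.** Replace the partial-date sentence in SAP 6.3 with rules to this effect:

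- A partial date that clearly shows a start before treatment stays before treatment; this takes precedence over what follows.
- Day missing, month and year both those of first dose: impute the first-dose date.
- Day missing, any other month: impute the first day of the recorded month.
- Month missing, same year as first dose: impute the first-dose date. Month missing, other year: impute 1 January of that year.
- Never impute a start later than the recorded stop date.

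Because the first-of-month rule still back-dates some late events, it would help to add that a bleed with an incomplete start date is assigned to the venography/day-12 window from its adjudicated or source-documented timing where that exists, and not from the imputed date alone.

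The cost is one short paragraph in the SAP and the matching derivation. The imputation rules need no new data, and the bleeding addition uses only timing already documented.

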5.8.3. Analysis of Clinical Laboratory Measurements

Laboratory measurements include clinical chemistry, hematology and urinalysis results, and will be converted to standard international units and US conventional units. Summaries of laboratory variables will include:

- Descriptive statistics of laboratory result and change from baseline by visit
- The number (n) and percentage (%) of participants with treatment-emergent PCSVs during study
- Shift tables based on baseline normal/abnormal may be used to present the results for parameters of interest

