Creatinine	$\geq 150 \mu\text{mol/L}$ (Adults) and baseline $< 100 \mu\text{mol/L}$ $\geq 30\%$ change from baseline $\geq 100\%$ change from baseline	Benichou C., 1994. 3 independent criteria
Blood Urea Nitrogen	$\geq 30 \text{ mmol/L}$ and baseline $< 17 \text{ mmol/L}$	One independent criteria
Sodium Hyponatremia Hypernatremia	$\leq 125 \text{ mmol/L}$ and baseline $> 129 \text{ mmol/L}$ $\geq 160 \text{ mmol/L}$ and baseline $< 155 \text{ mmol/L}$	Two independent criteria
Potassium Hypokalemia Hyperkalemia	$< 3 \text{ mmol/L}$ and baseline $\geq 3 \text{ mmol/L}$ $\geq 5.5 \text{ mmol/L}$ and baseline $< 4.9 \text{ mmol/L}$	FDA Feb 2005. Two independent criteria
Glucose Hypoglycaemia Hyperglycaemia	$\leq 3.9 \text{ mmol/L}$ and $< \text{LLN}$ and baseline $> 5.9 \text{ mmol/L}$ $\geq 11.1 \text{ mmol/L}$	ADA Jan 2008.
Albumin	$\leq 32 \text{ g/L}$ and baseline $> 35 \text{ g/L}$	
Hematology		
WBC	$< 2.0 \text{ Giga/L}$ and baseline $\geq 4.0 \text{ Giga/L}$ $\geq 16.0 \text{ Giga/L}$ and baseline $< 10 \text{ Giga/L}$	Increase in WBC: not relevant. *The default criteria. Summary by race (black and Non-black) are optional. To be interpreted only if no differential count available.
Neutrophils	$< 1.0 \text{ Giga/L}$ and baseline $\geq 2 \text{ Giga/L}$	International Consensus meeting on drug-induced blood cytopenias, 1991.
Eosinophils	$> 1 \text{ Giga/L}$ and baseline $\leq 0.4 \text{ Giga/L}$	Harrison- Principles of internal Medicine 17 th Ed., 2008.
Hemoglobin	$\leq 10 \text{ g/L}$ and baseline $> 12 \text{ g/L}$ *Decrease from Baseline $\geq 30\%$	Two criteria are independent. Criteria based upon decrease from baseline are more relevant than based on absolute value. Other categories for decrease from baseline can be used ($\geq 30 \text{ g/L}$, $\geq 40 \text{ g/L}$, $\geq 50 \text{ g/L}$). *based on expected post-operative changes

Parameter	PCSV Criteria	Comments and References
Hematocrit	≤ 0.32 v/v and baseline >0.38 v/v *Decrease from Baseline $\geq 30\%$	The first criteria is the follow up value. *based on expected post-operative changes
Platelets	<50 Giga/L and baseline ≥ 100 Giga/L ≥ 700 Giga/L and baseline <400 Giga/L	International Consensus meeting on drug-induced blood cytopenias, 1991. Two independent criteria
Vital signs		
HR	≤ 50 bpm ≥ 130 bpm	To be applied for all positions except STANDING.
SBP	≤ 95 mmHg and decrease from baseline ≥ 20 mmHg ≥ 165 mmHg and increase from baseline ≥ 20 mmHg	To be applied for all positions except STANDING.

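### SAP 11.3 lets hypoglycaemia be flagged only when baseline glucose exceeds 5.9 mmol/L, and SAP 6.3 and 11.3 give different eosinophil criteria

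*SAP*

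**What the plan says.** SAP 5.8.3 promises, for laboratory data, the number and percentage of "participants with treatment-emergent PCSVs during study". The criteria are tabulated in SAP 11.3.

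- **Glucose (SAP 11.3).** Hypoglycaemia needs three conditions joined by *and*: value at most 3.9 mmol/L, value below LLN, baseline above 5.9 mmol/L. Hyperglycaemia is a value of at least 11.1 mmol/L, with no baseline condition.
- **Eosinophils (SAP 11.3).** Value above 1 giga/L and baseline at most 0.4 giga/L. There is no ULN term.
- **Eosinophils (SAP 6.3, missing-data conventions).** As an example of a criterion built on a threshold and a normal range: "for eosinophils the PCSV is >0.5 giga/L", or above ULN if ULN is at least 0.5. It then adds: "When ULN is missing, the value 0.5 should be used".
- **Missing baselines (SAP 6.3).** "If a participant has a missing baseline value, this participant will be grouped in the category" that combines normal with missing.

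The SAP does not say whether 6.3 or 11.3 takes precedence. It defines treatment-emergent for adverse events (SAP 5.8.1) but not for PCSVs.

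**The concern.** A baseline clause in a PCSV table normally keeps out participants who were already abnormal, so that the count reflects change on study. The hypoglycaemia clause works differently. It keeps out everyone whose recorded baseline was 5.9 mmol/L or lower, whether or not that baseline was low. Programmed exactly as written, the row undercounts new low glucose values.

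For eosinophils the fault is an undetermined count rather than a known miscount. Two programmers following the same SAP could report different numbers.

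What is at stake is the accuracy of a descriptive safety table. The primary analysis, the sample size and the efficacy conclusions do not depend on it.

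**Working it through.** The plan states no figure to reproduce here. The check is logical, plus one calculation under assumptions.

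**1. Hypoglycaemia rule on a grid.** The inputs are the three conditions in SAP 11.3. LLN was set to 4.0 mmol/L for the check only, because the documents give no reference range. Post-baseline values tried were 2.0, 3.0, 3.5 and 3.9.

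| Baseline (mmol/L) | Flagged? |
|---|---|
| 4.0, 4.5, 5.0, 5.5, 5.9 | none of the four values |
| 6.0, 7.0 | all four values |
| missing, judged on the threshold alone | all four values |

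The rule demands a fall of more than 5.9 − 3.9 = 2.0 mmol/L (2.0/5.9 = 34%). A baseline of 5.0 falling to 2.8 is not counted. A baseline of 6.0 falling to 3.8 is counted if 3.8 is below LLN.

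**2. Share of an arm that cannot be flagged.** The planned arm size is 120 (SAP 2.2). Baseline glucose is assumed normal, with assumed means and SDs. Share ineligible = Φ((5.9 − mean)/SD).

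| Assumed mean (SD) | z | Eligible | Ineligible | Ineligible of 120 |
|---|---|---|---|---|
| 5.3 (0.6) | 1.00 | 0.159 | 0.841 | 101 |
| 5.6 (0.9) | 0.33 | 0.369 | 0.631 | 76 |
| 6.0 (1.3) | −0.08 | 0.531 | 0.469 | 56 |

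A wider grid (means 5.0 to 6.5, SDs 0.6 to 1.5) gives 16% to 93% ineligible, or 19 to 112 of 120.

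**3. Comparison with other low-side rows in SAP 11.3** (baseline clause divided by flag): potassium 3/3 = 1.0; sodium 129/125 = 1.03; albumin 35/32 = 1.09; glucose 5.9/3.9 = 1.51; WBC 4/2, neutrophils 2/1 and platelets 100/50 = 2.0. A wide gap alone therefore proves nothing. What matters is whom the clause bars. For platelets, inclusion criterion 4 (Protocol 7.2.1) requires a count above 150 K, so a baseline clause of at least 100 bars almost nobody. No entry criterion does the same for glucose.

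**4. Eosinophils, 6.3 against 11.3.** When ULN is missing or at most 0.5, the 6.3 cut-off is 0.5 and the ratio is 1.0/0.5 = 2.0. With ULN 0.6 it is 1.0/0.6 = 1.67, and with ULN 0.7 it is 1.0/0.7 = 1.43. The rules disagree in two regions:

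- Values above the 6.3 cut-off and up to 1.0. For example, 0.3 rising to 0.8 is flagged by 6.3 if ULN is missing or below 0.8, and never by 11.3.
- Values above 1.0 (and above ULN) with baseline above 0.4. For example, 0.45 rising to 1.5 is flagged by 6.3 if ULN is missing or below 1.5, and never by 11.3.

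**The case against.** **What stands.** The eosinophil figure in 6.3 is an example in a missing-data section, and 11.3 is the section that sets the criteria. The 11.3 row has no ULN term, so the fallback has nothing to act on. The likeliest explanation is a leftover example, and the repair is editorial. Even so, the sentence names the analyte, states its PCSV and gives a programming instruction, so it should not be left standing.

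Several rows also deliberately require a marked shift from baseline. Calling the glucose clause wrong assumes that many baselines of 5.9 or below are normal. The documents give no reference range, and the row cites a source not available here. That is why the size is shown as a range. It does not rescue the clause, which would still bar a large share of participants under most of the assumed distributions.

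**Stronger readings that the documents do not support.**

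- *Low glucose would go unseen.* The PCSV table is not the only laboratory output. SAP 5.8.3 also gives descriptive statistics by visit (with minimum and maximum, SAP 5) and optional shift tables. Protocol 10.1.1 provides for abnormal results to be reported as adverse events under stated conditions.
- *The eosinophil conflict affects the hypersensitivity AESI.* SAP 4.5.1 defines that AESI by moderate or severe reactions, and SAP 5.8.8 uses standardised MedDRA queries. Neither uses eosinophil counts.
- *Pre-existing hyperglycaemia will be counted as new.* The row has no baseline clause, but SAP 5.8.3 restricts the output to treatment-emergent PCSVs. Whether a value already at 11.1 or above before dosing counts depends on a term left undefined. The gap is one of definition, not a shown miscount.
- *47–84% of hypoglycaemic events will be missed.* The figure is the share of participants who cannot be flagged. Post-baseline chemistry is scheduled only at days 10 and 75, and nothing in the documents allows an estimate of events.

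**Conclusion.** The concern holds in a limited form. As written, the hypoglycaemia row cannot count a participant with a recorded baseline of 5.9 mmol/L or below, however low the later value. The one exception is a missing baseline, which SAP 6.3 groups with normal. It should be rare, because chemistry is scheduled at screening and before surgery. The ineligible share is 47–84% of an arm for the three assumed baselines, and 16–93% on the wider grid. Both ranges rest on assumed normal distributions.

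The two eosinophil statements conflict and no precedence is given. The gap is exactly twofold only when ULN is missing or at most 0.5 giga/L, and smaller for a higher ULN.

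The consequence is confined to the descriptive laboratory PCSV table. This is a minor but definite correction.

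**What to change.** Make three text edits to the SAP before database lock. SAP 1 allows documented revisions up to that point.

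1. **Hypoglycaemia row, SAP 11.3.** Replace the baseline clause with one that excludes only participants already low. Either require that the baseline did not itself meet the flag (not both at most 3.9 mmol/L and below LLN) or, more simply, that it was not below LLN. The simpler form is tighter where LLN exceeds 3.9: with LLN 4.1, a baseline of 4.0 passes the two-part clause but not the simpler one.
2. **Eosinophils.** Keep the 11.3 row as the criterion, and delete or align the example in 6.3.
3. **Treatment-emergent.** State in SAP 5.8.3 that a PCSV already met at baseline, such as glucose of at least 11.1 mmol/L, is not counted as treatment-emergent.

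The cost is the edits and the matching programming. No new data are needed, and no efficacy analysis changes.
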